12. I have problems completing daily household chores (e.g., cleaning, cooking, laundry, house maintenance)								
13. I have problems taking care of myself (e.g., bathing, dressing, shaving)								

14. I have problems participating in leisure activities (e.g., watching television, relaxing)							
15. I have problems participating in social activities (e.g., going out to eat, visiting friends)							
16. I have problems with work productivity							
PSYCHOLOGICAL SYMPTOMS	Check if Not Applicable	Not at all 0	A little bit 1	Somewhat 2	Quite a bit 3	Very much 4	Difficult To Understand
17. I have difficulty concentrating							
18. I have a decreased enjoyment of anal sexual activity							
19. I have a decreased enjoyment for any form of sexual activity other than anal sexual activity							
20. I have a decreased desire for anal sexual activity							
21. I have decreased desire for forms of sexual activity other than anal sexual activity							
22. I am worried about my condition getting worse							
23. I have anxiety							
24. I have depression							
25. I have problems with my intimate relationships							

Now let's quickly go through and have you tell me what your responses were to each of the 25 items [RECORD RESPONSES ON YOUR FORM]. Please let me know if you checked off 'Difficult to Understand' or 'Not Applicable' for any of the items.

Cognitive Interviewing Probes – General

First, for the statements that you responded to, was it easy to answer....

- All of the time
- Most of the time
- Some of the time
- None of the time

Were there any problems that made it difficult for you to answer the survey in general? If so, what were they?

Now let's go back and discuss any of those areas where you indicated that the statement was hard to understand. Putting aside issues that you have already told me about, what were the issues or problems that came up for you in those places?

(Some of the issues raised during this portion may probe specific issues that we are targeting, please make note of these to work toward not repeating these issues again in the interview)

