Cognitive Interviewing Probes – Instructions

Did you have any problems in understanding the instructions? If so, please describe these problems.

Below is a list of statements that other people diagnosed with anal HSIL and treated or actively monitored have said are important. Please check the box to select your answer based on your experiences in the past 7 days.

What does the word experiences mean to you as it is used in these instructions? Is there another word or phrase that you would prefer that we use?

Cognitive Interviewing Probes – Question-Specific

You were asked about PAIN as a possible symptom related to your Anal HSIL. Do you experience PAIN that is separate from ANAL PAIN or PAIN DURING BOWEL MOVEMENTS?

If so, how is the PAIN you experience different from ANAL PAIN or PAIN DURING BOWEL MOVEMENTS? Do you believe we should ask about all three types of PAIN?

What does ITCHING IN OR AROUND THE ANUS mean to you as it was used in this statement? Do you feel that ITCHING IN and ITCHING AROUND should be two separate statements?

If patient experiences DISCHARGE (WETNESS):

Which of the words DISCHARGE (WETNESS) do you prefer to describe this experience? Is there another word or phrase that you feel would better describe this experience?

What does BURNING SENSATION mean to you as it was used in this statement? Is there another word or phrase that you feel would better describe this experience?

What does PHYSICAL ABILITY TO MOVE AROUND mean to you as it was used in this statement? Is there another word or phrase that you feel would better describe this experience? If you were to choose between “moverse” and “movilizarse,” which word would you prefer?

What does PROBLEMS WITH SITTING mean to you as it was used in this statement? Is there another word or phrase that you feel would better describe this experience? Would you prefer that we use “difficulty” sitting?

What does DAILY HOUSEHOLD CHORES (CLEANING, COOKING, LAUNDRY, HOUSE MAINTENANCE) mean to you as it was used in this statement? Are there other examples that you feel would be better to describe this experience?

What does PROBLEMS TAKING CARE OF MYSELF (BATHING, DRESSING, SHAVING, ETC.) mean to you as it was used in this statement? Are there other examples that you feel would be better to describe this experience?

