12. Tengo problemas terminando las tareas de la casa (por ej., limpiar, cocinar, hacer la colada, llevar la casa)							

13. Tengo problemas con mi arreglo personal diario (por ej., bañándome, vistiéndome, afeitándome)							
14. Tengo problemas participando en actividades de ocio (por ej., mirar televisión, relajarme)							
15. Tengo problemas participando en actividades sociales (por ej., salir a comer, visitar amigos)							
16. Tengo problemas siendo productivo en el trabajo							
SÍNTOMAS PSICOLÓGICOS	Escoja si no aplica	Para nada 0	Un poco 1	Algo 2	Bastante 3	Muchísimo 4	Difícil de entender
17. Tengo dificultad concentrándome							
18. Me ha disminuido el placer de la actividad sexual anal							
19. Me ha disminuido el placer de cualquier forma de actividad sexual diferente a la actividad sexual anal							
20. Me ha disminuido el deseo por la actividad sexual anal							
21. Me ha disminuido el deseo por formas de actividad sexual diferentes a la actividad sexual anal							
22. Me preocupa que mi enfermedad empeore							
23. Tengo ansiedad							
24. Tengo depresión							
25. Tengo problemas con mis relaciones íntimas							

Ahora nos va a contar cuáles fueron sus respuestas para cada una de las 25 preguntas (REGISTRE LAS RESPUESTAS EN SU FORMULARIO). Por favor cuénteme si escogió “Difícil de entender” o “No aplica”.

Sondeo de la entrevista cognitiva – General

Primero, para las cosas que contestó, fue fácil de contestar....

- Todo el tiempo
- La mayoría del tiempo
- Algunas veces
- Nunca

¿Hubo algún problema que hizo difícil contestar la encuesta en general? Si sí, ¿qué?

Ahora examinemos lo que le pareció difícil de entender. Olvidándose de las cosas que ya me ha contado, ¿cuáles fueron los problemas que surgieron en esos momentos?

(Algunos de los asuntos planteados durante esta porción podrían hacer resaltar problemas específicos que forman parte de nuestro objetivo. Por favor tome nota de ellos para que no vuelvan a surgir durante la entrevista).

Sondeo de la entrevista cognitiva – Instrucciones

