¿Tuvo algún problema entendiendo las instrucciones? Si sí, por favor describa estos problemas.

*A continuación presentamos una lista de afirmaciones que otras personas diagnosticadas con HSIL (lesión precancerosa en el ano) y que han sido tratadas o monitoreadas activamente han dicho que son importantes. Por favor seleccione la casilla con su respuesta basándose en sus experiencias **en los últimos 7 días**.*

¿Qué significa para usted la palabra “experiencias” tal como se utiliza en estas instrucciones?
¿Preferiría que utilicemos alguna otra palabra o frase?

Sondeo de la entrevista cognitiva – Preguntas específicas

Le preguntaron sobre DOLOR como un síntoma posible relacionado con HSIL anal.

¿Experimenta DOLOR no vinculado con el DOLOR ANAL o DOLOR DURANTE LA DEFECACIÓN?

Si respondió que sí, ¿el DOLOR que usted siente es diferente al DOLOR ANAL o DOLOR DURANTE LA DEFECACIÓN? ¿Le parece que debemos preguntar sobre los tres tipos de DOLOR?

¿Qué quiere decir para usted PICAZÓN EN EL ANO O ALREDEDOR DEL ANO según se preguntó en esta afirmación? ¿Piensa que PICAZÓN EN y PICAZÓN ALREDEDOR deberían ser dos afirmaciones separadas?

Si el paciente experimenta SECRECIÓN (MOJADO):

¿Cuál palabra SECRECIÓN (MOJADO) prefiere para describir esta experiencia? ¿Existe otra palabra o frase que piensa que describiría mejor esta experiencia?

¿Qué significa para usted SENSACIÓN DE ARDOR según se usó en esta afirmación? ¿Existe otra palabra o frase que piensa que describiría mejor esta experiencia?

¿Qué significa para usted LA CAPACIDAD FÍSICA PARA MOVILIZARSE en esta afirmación? ¿Existe otra palabra o frase que piensa que describiría mejor esta experiencia? Si tuviera que elegir entre “moverse” o “movilizarse”, ¿cuál palabra elegiría?

¿Qué significa para usted TENER PROBLEMAS PARA SENTARSE en esta afirmación? ¿Existe otra palabra o frase que piensa que describiría mejor esta experiencia? ¿Preferiría que se usara la frase “dificultad para sentarse”?

¿Qué significa para usted TAREAS DE LA CASA DIARIAS (LIMPIAR, COCINAR, HACER LA COLADA, LLEVAR LA CASA) según se usó en esta afirmación? ¿Hay otros ejemplos que piensa que funcionarían mejor para describir esta experiencia?

¿Qué significa para usted PROBLEMAS PERSONALES DIARIOS (BAÑÁNDOSE, VISTIÉNDOSE, AFEITÁNDOSE, ETC.) según se usó en esta afirmación? ¿Hay otros ejemplos que piensa que funcionarían mejor para describir esta experiencia?

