APPENDIX XI: ANCHOR HEALTH-RELATED SYMPTOM INDEX – ENGLISH

Below is a list of statements that other people diagnosed with anal HSIL (pre-cancer lesion in the anus) and treated or actively monitored have said are important. Please check the box to select your answer based on your experiences in **the past 7 days**.

PHYSICAL SYMPTOMS	Check if Not Applicable	Not at all 0	A little bit 1	Somewhat 2	Quite a bit 3	Very much 4	Difficult to Understand
1. I have anal pain							
2. I have pain other than anal pain							
3. I have pain during bowel movements							
4. I have constipation							
5. I have bleeding from the anus							
6. I have itching in or around the anus							
7. I have discharge (wetness) in my anal area							
8. I have burning sensations in the anal area							
9. I have urgency for bowel movements							
PHYSICAL IMPACTS	Check if Not Applicable	Not at all 0	A little bit 1	Somewhat 2	Quite a bit 3	Very much 4	Difficult to Understand
10. I have problems with my physical ability to move around							
11. I have problems with sitting							
12. I have problems completing daily household chores (e.g., cleaning, cooking, laundry, house maintenance)							
13. I have problems taking care of myself (e.g., bathing, dressing, shaving)							
14. I have problems participating in leisure activities (e.g., watching television, relaxing)							

15. I have problems participating in social activities (e.g., going out to eat, visiting friends)							
16. I have problems with work productivity							
PSYCHOLOGICAL SYMPTOMS	Check if Not Applicable	Not at all 0	A little bit 1	Somewhat 2	Quite a bit 3	Very much 4	Difficult to Understand
17. I have difficulty concentrating							
18. I have a decreased enjoyment of anal sexual activity							
19. I have a decreased enjoyment for any form of sexual activity other than anal sexual activity							
20. I have a decreased desire for anal sexual activity							
21. I have decreased desire for forms of sexual activity other than anal sexual activity							
22. I am worried about my condition getting worse							
23. I have anxiety							
24. I have depression							
25. I have problems with my intimate relationships							

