APPENDIX XII: ANCHOR HEALTH-RELATED SYMPTOM INDEX – SPANISH

ÍNDICE DE SÍNTOMAS RELACIONADOS CON LA SALUD ANCHOR

A continuación presentamos una lista de afirmaciones que otras personas diagnosticadas con HSIL (lesión precancerosa en el ano) y que han sido tratadas o monitoreadas activamente han dicho que son importantes. Por favor seleccione la casilla con su respuesta basándose en sus experiencias en **los últimos 7 días**.

SÍNTOMAS FÍSICOS	Escoja si no aplica	Para nada 0	Un poco 1	Algo 2	Bastante 3	Muchísimo 4	Difícil de entender
1. Tengo dolor anal							
2. Tengo dolor pero no en el área anal							
3. Tengo dolor cuando entro al baño a defecar							
4. Tengo estreñimiento							
5. Tengo sangrado del ano							
6. Tengo picazón en el ano o alrededor del ano							
7. Tengo una secreción (mojado) en el área anal							
8. Tengo sensación de ardor en el área anal							
9. Siento urgencia de entrar al baño a defecar							
IMPACTOS FÍSICOS	Escoja si no aplica	Para nada 0	Un poco 1	Algo 2	Bastante 3	Muchísimo 4	Difícil de entender
10. Tengo problemas con mi capacidad física para movilizarme							
11. Tengo problemas para sentarme							
12. Tengo problemas terminando las tareas de la casa (por ej., limpiar, cocinar, hacer la colada, administrar la casa)							
13. Tengo problemas con mi arreglo personal diario (por ej., bañándome, vistiéndome, afeitándome)							
14. Tengo problemas participando en actividades de ocio (por ej., mirar televisión, relajarme)							

15. Tengo problemas participando en actividades sociales (por ej., salir a comer, visitar amigos)							
16. Tengo problemas siendo productivo en el trabajo							
SÍNTOMAS PSICOLÓGICOS	Escoja si no aplica	Para nada 0	Un poco 1	Algo 2	Bastante 3	Muchísimo 4	Difícil de entender
17. Tengo dificultad concentrándome							
18. Me ha disminuido el placer de la actividad sexual anal							
19. Me ha disminuido el placer de cualquier forma de actividad sexual diferente a la actividad sexual anal							
20. Me ha disminuido el deseo por la actividad sexual anal							
21. Me ha disminuido el deseo por formas de actividad sexual diferentes a la actividad sexual anal							
22. Me preocupa que mi enfermedad empeore							

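### Spanish item 13 adds a daily limit that the English item lacks and leans towards grooming, and its interview probe does not quote it, so the slip may go unnoticed (minor)

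*Protocol*

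**What the plan says.** The Protocol Synopsis presents the Spanish text as a translation of the instrument studied in English speakers. Section 4.0 gives the purpose of the interviews as establishing its content validity in Spanish.

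The English item 13 is the same in Appendix VII ("13. I have problems taking care of myself (e.g., bathing, dressing, shaving") and Appendix XI ("I have problems taking care of myself (e.g., bathing, dressing, shaving"). The Spanish item 13 is the same in Appendix VIII ("13. Tengo problemas con mi arreglo personal diario (por ej., bañándome, vistiéndome, afeitándome") and Appendix XII ("Tengo problemas con mi arreglo personal diario (por ej., bañándome, vistiéndome, afeitándome").

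The English interview probe repeats its item's concept: "What does PROBLEMS TAKING CARE OF MYSELF (BATHING, DRESSING, SHAVING, ETC.) mean to you as it was used in this statement". The Spanish probe asks what the participant understands by "PROBLEMAS PERSONALES DIARIOS (BAÑÁNDOSE, VISTIÉNDOSE, AFEITÁNDOSE, ETC.) según se usó en esta afirmación".

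The neighbouring item 12 reads "I have problems completing daily household chores" in English and "Tengo problemas terminando las tareas de la casa" in Spanish.

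**The concern.** A translated item should ask the same question as its source. Here the Spanish departs in two ways. It adds a daily limit, which is plain on the page. It also replaces taking care of oneself with *arreglo personal*, whose ordinary sense is nearer to grooming; that is a judgement about language. No other item asks about self-care, so no neighbouring item makes up for a shift in meaning here.

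What is at stake is content equivalence, which is what the study is meant to deliver before the index goes into ANCHOR for validity and reliability testing. If Round 1 does not expose the difference, it can pass into the final Spanish version, because Section 2.3 makes Rounds 2 and 3 conditional on need.

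**Working it through.** The plan states no figure on this point, so the check is a side-by-side reading.

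| Element | English (Appendices VII, XI) | Spanish (Appendices VIII, XII) |
|---|---|---|
| Item 13 stem | taking care of oneself | *arreglo personal* (personal grooming) |
| Item 13 frequency | none | *diario* (daily) |
| Item 13 examples | bathing, dressing, shaving | the same three |
| Item 13 probe | repeats the item's stem | daily personal problems |
| Item 12 frequency | daily | none |

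**Step 1: frequency limit.** Neither English version of item 13 says daily. Both Spanish versions do.

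**Step 2: where the word belongs.** English item 12 says daily and Spanish item 12 does not. The Spanish probe for item 12 (Appendix VIII) does carry the daily qualifier, so the word was recognised as part of that concept. Its absence from Spanish item 12 and its presence in Spanish item 13 fit a word that moved one line down. The protocol gives no reason for either change.

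**Step 3: stem.** The English stem is general and the activities are only examples of it. The Spanish stem leans towards appearance, but bathing and dressing are basic self-care, and a respondent reads stem and examples together. The overlap is therefore large.

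**Step 4: would the interview find it?**
- The Spanish probe names a wording that is not in the item the participant has just answered, so the reply would not show how *arreglo personal* was understood. It also keeps daily and never offers the self-care concept.
- The item 13 probe asks for meaning and for better examples. It does not ask for another word or phrase, as the probes for items 8, 10 and 11 do.
- The box for items that are hard to understand detects unclear wording. *Arreglo personal diario* is clear, so it is unlikely to be ticked.
- Section 3.1.6 selects people with limited English proficiency, and they are interviewed on the Spanish text. They are unlikely to notice a departure from the English.

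**Step 5: extent.** Items 10 to 16 are the physical-impact section, 16 − 10 + 1 = 7 items. Item 13 is 1/25 = 4% of the index and 1/7 = 14% of that section. These are counts of items, not estimates of bias.

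**The case against.** The strongest reply is that testing this wording is what the study is for. The Synopsis calls the Round 1 text an initial draft, with revised items to follow, and participants can mark difficult items, answer an item 13 probe and suggest improvements at the end. This stands in part: a draft may contain imperfect wording. It does not fully answer the point, because the one probe aimed at item 13 does not quote it. Sections 2.3 and 4.0 also call the measure finalized.

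A second reply is that the shared examples define the item, and that *diario* adds little when the named activities are routine and both versions ask about the past 7 days. This stands, and it is why the defect is modest.

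A third reply is that the protocol does not describe how the translation was made, so a deliberate adaptation cannot be excluded, and that preferring *cuidado personal* without respondent evidence is only another opinion. That is fair, and the fix therefore leaves the stem to the translators and puts both stems to participants.

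A reader might go further and infer that English speakers count care of the treated area under item 13 while Spanish speakers would not, so that Spanish scores would be lower for the same problem. The documents do not support this. Section 2.2 describes treatments, side effects and healing but does not link care of the treated area to item 13, and washing could fall under the bathing example. No data give a direction or a size, and Section 5.0 plans no formal statistical analysis, so no score comparison is planned in this study.

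**Conclusion.** The point holds as a minor equivalence defect. The added daily limit, the differing item 12 and the probe that does not match its item are facts of the text. That the stem is narrower is a linguistic judgement, and that *diario* is a slip is an inference from item 12 and its probe; neither is proved. The effect is confined to one item whose examples are identical in the two languages, and nothing in the documents allows its effect on responses to be estimated. What makes it worth correcting is the low chance that Round 1, as scripted, would reveal it, set against an almost free remedy.

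**What to change.** Before Round 1:

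1. Remove *diario* from item 13 in Appendices VIII and XII.
2. Have the translators align the stem with the English self-care concept, for example *cuidado personal*, or record why an adaptation was chosen.
3. Make the item 13 probe in Appendix VIII quote the item exactly.
4. Add a choice between *arreglo personal* and *cuidado personal* to that probe, as the script already does for *moverse* and *movilizarse* in item 10, so that respondents settle the stem.
5. While the text is open, have the translators check whether item 12 should carry the daily qualifier, as its English source and its own Spanish probe do.

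The cost is one item in two appendices and one probe, plus a translator's check of item 12. No participants are added and the interview is barely longer. Done before Round 1, it avoids spending the 20 planned interviews on a probe that does not test the printed item.

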There is a paucity of data on symptoms and concerns of persons diagnosed and treated for anal HSIL. In one prospective study from the ANCHOR PI’s research team¹³, a small sample (n=37; 29 of whom were HIV-positive; mean age of 45.8 years) of persons diagnosed with HSIL were treated with surgical excision and followed every 3-6 months for a mean of 32 months. The primary aim of the study was to demonstrate the safety and efficacy of high-resolution anoscopy and surgical treatment for diagnosed HSIL. A specific set of symptoms and concerns were assessed: Uncontrolled pain, persistent bleeding, perianal abscess formation, late development of anal stenosis, and alteration in anal continence or sexual function. Approximately half of the patients (16/29) reported uncontrolled pain after the procedure that lasted for a mean of 2.9 weeks (range 1 to 120 days). Most of the pain experienced was associated with bowel movements. No patients required reoperation for abscess or bleeding, or experienced clinically significant stenosis or incontinence to formed stool. Twenty-four (83%) of 29 patients reported receptive anal intercourse before surgery, and 21 of these 24 resumed receptive anal intercourse after an average duration of 5.7 months. Those who did not resume receptive anal intercourse did so for reasons not clearly attributable to surgery. These data, although emanating from one small study using only one of several treatment modalities, suggest that HRQoL concerns are substantial after treatment for anal HSIL. It is important to assess physical symptoms and concerns in those living with or treated for anal HSIL, as these may be important considerations in treatment decision-making for patients and their physicians, especially in the context of an ANCHOR finding of equivalent effectiveness of active treatment vs. active monitoring at the trial’s end.

A second study examined psychological symptoms associated with anal cancer screening (high resolution anoscopy) in 104 HIV-positive MSM in primary care and HIV clinics in Canada¹⁴. Data were collected with multiple standardized measures of psychological distress at four time points during the study: time 1 (within a week before the initial visit),

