¿Qué significa para usted PROBLEMAS PARTICIPANDO EN ACTIVIDADES DE OCIO (MIRANDO TELEVISIÓN, RELAJÁNDOSE) según se usó en esta afirmación? ¿Le plantea alguna dificultad la palabra “ocio”? ¿Preferiría que se utilice la frase “actividades que realiza en su tiempo libre”? ¿Hay otros ejemplos que piensa que funcionarían mejor para describir esta experiencia?

¿Qué significa para usted PROBLEMAS PARTICIPANDO EN ACTIVIDADES SOCIALES (SALIR A COMER, VISITAR AMIGOS) según se usó en esta afirmación? ¿Hay otros ejemplos que piensa que funcionarían mejor para describir esta experiencia?

¿Piensa que es importante preguntar sobre ACTIVIDADES DE OCIO y ACTIVIDADES SOCIALES? Si se le preguntara tan solo una de ellas, ¿cuál seleccionaría? ¿Por qué?

¿Qué significa para usted PROBLEMAS CON LA PRODUCTIVIDAD EN EL TRABAJO según se usó en esta afirmación? (PREGUNTE SI EL PARTICIPANTE NO ESTÁ TRABAJANDO) ¿Hay alguna otra palabra o frase que usted cree que describiría mejor esta experiencia?

¿Qué significa para usted DIFICULTAD CONCENTRÁNDOSE según se usó en esta afirmación?

¿Qué significa para usted DISMINUCIÓN DE PLACER DE LA ACTIVIDAD SEXUAL ANAL según se usó en esta afirmación?

¿Preferiría que se utilice la frase “placer físico” en vez de “placer” al preguntar sobre esta experiencia?

¿En qué se diferencia de DISMINUCIÓN DE PLACER POR OTRAS FORMAS DE ACTIVIDAD SEXUAL? ¿Piensa que es necesario que se le pregunte sobre ambos conceptos? Si se le preguntara tan solo uno de ellos, ¿cuál seleccionaría? ¿Por qué?

¿Qué significa para usted DISMINUCIÓN DE DESEO POR ACTIVIDAD SEXUAL ANAL según se usó en esta afirmación?

¿En qué se diferencia de DISMINUCIÓN DE DESEO POR OTRAS FORMAS DE ACTIVIDAD SEXUAL? ¿Piensa que es necesario que se le pregunte sobre ambos conceptos? Si se le preguntara tan solo uno de ellos, ¿cuál seleccionaría? ¿Por qué?

¿Qué significa para usted ESTOY PREOCUPADO QUE MI ENFERMEDAD EMPEORE según se usó en esta pregunta?

¿Qué significa para usted RELACIONES ÍNTIMAS según se usó en esta pregunta?

¿Preferiría que preguntásemos sobre la “intimidad afectiva con otras personas” en vez de “relaciones íntimas”?

Sondeo de la entrevista cognitiva – Comprensión de la escala de respuesta

En general, ¿qué tan difícil fue seleccionar respuestas para las afirmaciones que le pedían que seleccionara, para nada, un poco, algo, bastante, mucho? (DE EJEMPLOS DEL CUESTIONARIO)

- PARA NADA difícil
- UN POCO difícil
- ALGO difícil
- MUY difícil

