Para lo siguiente debe encontrar un ítem para el que el paciente contestó con un 2 y determinar de qué manera difirió de una respuesta 1 o 3. También debe encontrar un ítem para el que el paciente contestó con un 3 y determinar de qué manera difirió de una respuesta 2 o 4.

Usted contestó (2). ¿Cómo llegó a esa respuesta? ¿Por qué es una mejor respuesta que (x+1)? ¿Por qué (x) es una mejor respuesta que (x-1)?

Usted contestó (3). ¿Cómo llegó a esa respuesta? ¿Por qué es una mejor respuesta que (x+1)? ¿Por qué (x) es una mejor respuesta que (x-1)?

¿Hubo algunas otras palabras en las opciones de respuesta que eran confusas o difíciles de entender? Si sí, ¿cuáles?

Sondeo de la entrevista cognitiva – Período recordatorio

¿Qué tan fácil o difícil fue pensar en sus experiencias en los últimos 7 días? ¿Existe un mejor período de tiempo para considerar sus experiencias?

Respuestas de resumen

Ahora que ha respondido todo, me gustaría hacerle un par de preguntas finales sobre la entrevista en su totalidad. Recuerde que tan solo nos interesa mejorar la encuesta, por lo que si algo le resultó confuso o difícil de contestar asegúrese de decirlo—eso es exactamente lo que queremos averiguar.

- *¿Le pareció difícil esta entrevista?*
- *¿Le pareció que la entrevista fue demasiado larga?*
- *¿Alguna afirmación en la encuesta sobresalió por ser particularmente difícil para usted?*
- *¿Hay algo más que le gustaría que supiéramos sobre este cuestionario? ¿Tiene alguna sugerencia para mejorarlo para otras personas?*

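### Spanish items 18–21 change tense from the English under a 7-day recall, and the interview script is poorly placed to show how participants read them

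*Protocol*

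**What the plan says.** The English index (Appendix XI) words items 18–21 as conditions the respondent has now: item 18 is "I have a decreased enjoyment of anal sexual activity" and item 20 is "I have a decreased desire for anal sexual activity". The Spanish index (Appendix XII) renders them in the present perfect: item 18 is "Me ha disminuido el placer de la actividad sexual anal" and item 20 is "Me ha disminuido el deseo por la actividad sexual anal". Items 19 and 21 follow the same pattern, and the interview script (Appendix VIII) carries the same wording, for example item 21, "Me ha disminuido el deseo por formas de actividad sexual diferentes a la actividad sexual anal".

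All 25 items are answered from the participant's experiences in the last 7 days, on a scale from *Para nada* (0) to *Muchísimo* (4). The Spanish script asks an open meaning question for item 20, "Qué significa para usted DISMINUCIÓN DE DESEO POR ACTIVIDAD SEXUAL ANAL según se usó en esta afirmación", with a matching one for item 18. On recall it asks, for the questionnaire as a whole, "Qué tan fácil o difícil fue pensar en sus experiencias en los últimos 7 días", and then whether another period would be better.

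Sections 2.3 and 4.0 state the aim of the interviews: to establish the content validity of the Spanish measure. Section 1.1 says the index will then be validated within ANCHOR.

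**The concern.** A verb of change in the perfect, answered over a bounded window, can be taken as asking whether the change happened inside the window. Suppose a participant's desire fell after treatment three months ago and has stayed low. On that reading the participant could reasonably answer *Para nada*. On the other reading, that desire is now reduced, the same person would give a high score. The English phrasing, which names a condition held now, is less open to the first reading.

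These four items are the only ones on sexual enjoyment and desire. If some Spanish-speaking respondents read them as events, scores on this part of the index would not mean the same thing in the two languages once the measure is used in ANCHOR. The interviews are where this should come to light. A participant who takes the event reading, however, finds the item easy and has no reason to mark it as difficult to understand.

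**Working it through.** The protocol gives no figure to reproduce on this point; Section 5.0 foresees no formal statistical analysis. The check is a comparison of texts, a count and one illustration.

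**1. Items side by side (Appendices XI and XII)**

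| Item | English | Spanish |
|---|---|---|
| 18 | "I have a decreased enjoyment of anal sexual activity" | "Me ha disminuido el placer de la actividad sexual anal" |
| 20 | "I have a decreased desire for anal sexual activity" | "Me ha disminuido el deseo por la actividad sexual anal" |

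The English has *have* plus a noun phrase, a present state. The Spanish says literally that the pleasure or desire has decreased.

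**2. Count of verb forms in the Spanish index**

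- *Tengo*: items 1–8, 10–17 and 23–25, so 8 + 8 + 3 = 19.
- *Siento*: item 9. *Me preocupa*: item 22. Present tense in total: 19 + 1 + 1 = 21.
- Present perfect: items 18–21, so 4, and 4/25 = 16%.
- English items in the present perfect: 0 of 25.

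The four items therefore differ both from their source and from the rest of the Spanish form.

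**3. What the Spanish script (Appendix VIII) could detect**

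- *Meaning probes, items 18 and 20.* They restate the item with the noun *disminución*, so the verb form the participant answered is not what is read out.
- *Items 19 and 21.* They are asked only how they differ from 18 and 20, whether both are needed, and which the participant would keep. There is no meaning probe.
- *Answer-process probes.* The interviewer picks one item answered 2 and one answered 3 and asks how the answer was reached. The answer expected from the event reading is 0, which these probes never select.
- *Recall probe.* It is general and does not ask what a decrease was measured against.
- *Probes asking for a comparison time:* none.
- *Later recovery.* Under Sections 3.4.2 and 7.1, recordings are destroyed within 48 business hours and not transcribed, so a reading missed in the notes is lost.

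**4. How many participants the ambiguity could touch (illustration only)**

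Section 3.1.4 allows treatment up to nine months back: 9 × 30.44 = 274 days. Assume treatment dates are spread evenly over that time and that any decrease starts at treatment. The start then falls within the 7-day window for 7/274 = 2.6% of treated participants. If all were instead treated within the last three months (3 × 30.44 = 91 days), the share would be 7/91 = 7.7%. Under either assumption, most lasting decreases would have begun before the window. This describes who could meet the ambiguity; it does not estimate how many misread the item.

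**The case against.** The strongest reply has four parts.

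- **The Spanish perfect can express a result that still holds.** The instruction asks for an answer based on experiences in the last 7 days, not for a change during them, so someone whose desire stayed low all week can endorse the item. This stands. The event reading is possible, not established.
- **The missing comparison point is not a product of translation.** English *decreased* also implies an unnamed earlier level, the English script (Appendix VII) has no probe for it, and its probes are noun phrases too. This stands: that gap is shared and is no evidence of a difference between the languages. The tense change is the part peculiar to the Spanish.
- **The interviews exist to test wording, over up to three rounds.** The open meaning probes on items 18 and 20 point back to the statement, and the recall probe or the difficulty column might bring the issue out. This stands in part: the script could find the problem, but by chance. Section 2.3 makes Rounds 2 and 3 conditional on need, so a problem not noticed in Round 1 prompts no revision.
- **A replacement such as *Tengo menos deseo* is also comparative and untested.** This stands, and it argues against substituting a new wording before any participant has commented.

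A reader might also infer from the background in Section 2.3, where "21 of these 24 resumed receptive anal intercourse after an average duration of 5.7 months", that most participants carry a lasting loss of desire. The documents do not support that. The figure concerns resumed behaviour after surgery in one small study, not desire, enjoyment or the other treatment modalities. It makes impact beginning well before the window plausible, and no more.

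**Conclusion.** The concern holds in a limited form. Items 18–21, four of 25, differ in tense from the English and from the rest of the Spanish index. With a 7-day recall this leaves open a reading under which a lasting, earlier decrease is scored 0, and the script has no probe aimed at it.

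A reader might go further and infer that the translation turns a state into an event, that *Para nada* is the correct answer for a lasting decrease, or that Spanish scores will be systematically lower. The documents show none of these. Frequency of misreading, and hence any effect on scores, is unknown; the 2.6% and 7.7% figures depend on assumed treatment dates and do not measure it. The conclusion rests on the item and probe texts and on the linguistic judgement that both readings are available. It supports a cheap improvement to the interview, not a finding that the items are wrong.

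**What to change.** In Appendix VIII, and in Appendix VII for parity, add a follow-up for items 18–21:

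- Read the item back exactly as worded, with its verb, whatever scale answer was given, 0 included.
- Ask what time the participant compared with, and whether they thought of a change during the last 7 days or of how they felt during those days. For example: *¿Comparado con cuándo? ¿Pensó en un cambio durante los últimos 7 días o en cómo se sintió durante esos días?*
- In the Spanish script, offer a state wording parallel to the other items, such as *Tengo menos deseo…* or *Tengo menos placer…*, for the participant to compare with the current text, as the script already does for *moverse* and *movilizarse*.

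Record the reading taken for each of the four items in the interview summary, since the recording will not be kept. If the event reading appears in Round 1, revise items 18–21 in Appendices VIII and XII and test the revision in Round 2.

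The cost is a short script edit before Round 1 and about one extra minute per interview. No item needs rewording beforehand.
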